APPENDIX III - Case Report Forms

Data will be collected on electronic case report forms (eCRFs). The eCRFs will be made available before the study starts enrollment.

END OF MitraClip XTR PMCF Protocol

APPENDIX II: ABBREVIATIONS AND ACRONYM

A2-P2	Second location on anterior and posterior leaflets
ACCESS	ACCESS-EU Study
AE	Adverse Event
APS	Acute Procedural Success
ASD	Atrial Septal Defect
CDS	Clip Delivery System
CE	Conformité Européene
CEC	Clinical Events Committee
Co-PIs	Co-Primary Investigators
CRF	Case Report Form
CV	Cardiovascular
CVA	Cardiovascular Accident
DC	Delivery Catheter
DD	Device Deficiency
DM	Device Malfunction
DMR	Degenerative Mitral Regurgitation
DVT	Deep venous thrombus
EC	Ethics Committee
ECG	Electrocardiogram
eCRF	Electronic Case Report Form
EDC	Electronic Data Capture
EROA	Effective Regurgitant Orifice Area
EU	European Union
Euroscore	European System for Cardiac Operative Risk Evaluation
EVEREST II	The EVEREST II Study
EXPAND	The MitraClip EXPAND Study
FDA	U.S. Food and Drug Administration
FMR	Functional Mitral Regurgitation
GCP	Good Clinical Practice
GRASP	The GRASP Registry
HIPAA	Health Insurance Portability and Accountability Act
HRR	High Risk Registry (part of EVEREST II)
ICF	Informed Consent Form
IFU	Instructions for Use
IRB	Institutional Review Board
IVC	Inferior Vena Cava
KCCQ	Kansas City Cardiomyopathy Questionnaire
LVOT	Left Ventricle Outflow Tract

MAE	Major Adverse Event
MitraClip NT	MitraClip NT System
MitraClip NTR	MitraClip NTR System (new delivery system)
MitraClip XTR	MitraClip XTR System (new delivery system and longer clip arms)
MOPs	Manual of Operations
MR	Mitral Regurgitation
NYHA	New York Heart Association
PMCF	Post Market Clinical Follow-Up
QOL	Quality of Life
RCT	Randomized Controlled Trial
SAE	Serious Adverse Event
SAP	Statistical Analysis Plan
SAX	Short Axis
SGC	Steerable Guide Catheter
SLDA	Single leaflet device attachment
TEE	Transcatheter Esophageal Echocardiogram
TIA	Transient Ischemic Attack
TR	Tricuspid Regurgitation
TRAMI	Transcatheter Mitral Valve Interventions Study
TTE	Transcatheter Thoracic Echocardiogram
TVT	Transcatheter Valve Treatment Registry
UADE	Unanticipated Adverse Device Event
USADE	Unanticipated Serious Adverse Device Event

APPENDIX III: DEFINITIONS

DEATH (All Cause)

All deaths regardless of cause. Death is further divided into 2 categories

1. CARDIOVASCULAR DEATH (VARC)

Per the Valve Academic Research Consortium (VARC)⁵ as any one of the following:

- Any death due to proximate cardiac cause (e.g. MI, cardiac tamponade, worsening heart failure)
- Unwitnessed death and death of unknown cause
- All procedure-related deaths, including those related to a complication of the procedure or treatment for a complication of the procedure
- Death caused by non-coronary vascular conditions such as cerebrovascular disease, pulmonary embolism, ruptured aortic aneurysm, dissecting aneurysm, or other vascular disease

3. NON-CARDIOVASCULAR DEATH

Any death not covered by the VARC definitions of Cardiovascular Death, such as death caused by infection, malignancy, sepsis, pulmonary causes, accident, suicide, or trauma.

DEVICE EMBOLIZATION

Detachment of the deployed MitraClip from the leaflets as assessed by the study site.

DEVICE THROMBOSIS

Formation of an independently moving thrombus on any part of the MitraClip evidenced by echocardiography or fluoroscopy. If the MitraClip is explanted or an autopsy is performed, this diagnosis should be confirmed.

ENDOCARDITIS

A diagnosis of endocarditis based on the following Duke criteria, from The ACC/AHA Guidelines for the Management of Patients with Valvular Heart Disease, JACC, Vol 32, No.5, November 1, 1998:pg1541, Table 21)

Endocarditis is based on the confirmation of either Pathological Criteria or Clinical Criteria.

Diagnosis for Clinical Criteria of Endocarditis must at least meet 1 of the following combinations:

- 2 major criteria or
- 1 major plus 3 minor criteria or
- 5 minor criteria

Pathological Criteria

Microorganisms: culture or histology in a vegetation, in a vegetation that has embolized, or in an intracardiac abscess, OR

Pathological lesions: vegetation or intracardiac abscess present, confirmed by histology showing active endocarditis

OR

Clinical Criteria**Major Criteria**Persistently positive blood cultures:

Typical organisms for endocarditis: *Streptococcus viridans*, *S bovis*, “HACEK” group, community acquired *Staphylococcus aureus* or enterococci, in the absence of a primary focus

Persistent bacteremia:

≥ 2 positive cultures separated by ≥12 hours or ≥ 3 positive cultures ≥ 1 h apart or 70% blood culture samples positive if ≥ 4 are drawn

Evidence of endocardial involvement

Positive echocardiogram
Oscillating vegetation
Abscesses
Valve perforation
New partial dehiscence of prosthetic valve
New valvular regurgitation

Minor CriteriaPredisposing heart condition:

Mitral Valve Prolapse, bicuspid aortic valve, rheumatic or congenital heart disease, intravenous drug use

FeverVascular phenomena:

Major arterial emboli, septic pulmonary emboli, mycotic aneurysm, intracranial hemorrhage, Janeway lesions

Immunologic phenomena

Glomerulonephritis, Osler's nodes, Roth spots, and rheumatoid factor

Positive blood culture: not meeting major criteriaEchocardiogram: positive but not meeting major criteria**HOSPITALIZATION (ALL-CAUSE)**

Defined as admission to inpatient unit or ward in the hospital for at least 24 hours, including emergency department stay. Excludes hospitalizations planned for pre-existing conditions, unless there is worsening in the baseline condition.

HEART FAILURE HOSPITALIZATION

Defined as an event that meets the following criteria:

D. Requires hospitalization with treatment in any inpatient unit or ward in the hospital for at least 24 hours, including emergency department stay,

AND

E. Subject has clinical signs and/or symptoms of heart failure, including new or worsening dyspnea, orthopnea, paroxysmal nocturnal dyspnea, increasing fatigue, worsening functional capacity or activity intolerance, or signs and/or symptoms of volume overload,

AND

- F. Results in intravenous (e.g, diuretic or vasoactive therapy) or invasive (e.g., ultrafiltration, IABP, mechanical assistance) treatment for heart failure.

For the purpose of this protocol, overnight stays at nursing home facilities, physical rehab or extended care facilities, including hospice, do not meet the protocol definition of hospitalization.

OTHER CARDIOVASCULAR HOSPITALIZATION

Defined as treatment in any inpatient unit or ward in the hospital for at least 24 hours, including emergency department stay for conditions such as coronary artery disease, acute myocardial infarction, hypertension, cardiac arrhythmias, cardiomegaly, pericardial effusion, atherosclerosis and peripheral vascular disease, not related to heart failure as defined.

NON-CARDIOVASCULAR HOSPITALIZATION

Hospitalizations that are not heart failure or other cardiovascular hospitalizations, as defined above, will be categorized as non-cardiovascular hospitalizations.

MAJOR ADVERSE EVENT (MAE)

MAE defined as a composite of all-cause Death, MI, Stroke, or non-elective CV surgery for device related complications (CEC adjudicated)

MAJOR BLEEDING

Major bleeding is defined as bleeding \geq Type 3 based on a modified Bleeding Academic Research Consortium (BARC)³⁷ definition:

- Type 3
 - Type 3a
 - Overt bleeding plus hemoglobin drop of 3 to <5 g/dL* (provided hemoglobin drop is related to bleed)
 - Any transfusion with overt bleeding
 - Type 3b
 - Overt bleeding plus hemoglobin drop ≥ 5 g/dL* (provided hemoglobin drop is related to bleed)
 - Cardiac tamponade
 - Bleeding requiring surgical intervention for control (excluding dental/nasal/skin/hemorrhoid)
 - Bleeding requiring intravenous vasoactive agents
 - Type 3c
 - Intracranial hemorrhage (does not include microbleeds or hemorrhagic transformation, does include intraspinal)
 - Subcategories confirmed by autopsy or imaging or lumbar puncture
 - Intraocular bleed compromising vision
- Type 4: CV Surgery-related bleeding
 - Perioperative intracranial bleeding within 48 h
 - Reoperation after closure of sternotomy for the purpose of controlling bleeding
 - Transfusion of ≥ 5 U whole blood or packed red blood cells within a 48-h period†
 - Chest tube output ≥ 2 L within a 24-h period
- Type 5: Fatal bleeding
 - Type 5a

³⁷ Mehrana R, Rao SV, et al. Standardized bleeding definitions for cardiovascular clinical trials: a consensus report from the Bleeding Academic Research Consortium. *Circulation* 2011;123:2736-2747.

- Probable fatal bleeding; no autopsy or imaging confirmation but clinically suspicious
- Type 5b
 - Definite fatal bleeding; overt bleeding or autopsy or imaging confirmation

*Corrected for transfusion (1 U packed red blood cells or 1 U whole blood=1 g/dL hemoglobin)

†Cell saver products are not counted

MAJOR VASCULAR COMPLICATION

Any major complication, relating to, or affecting, the circulatory system as a result of the MitraClip procedure, including new onset of any of the following:

- Hematoma at access site >6 cm.;
- Retroperitoneal hematoma;
- Arterio-venous fistula;
- Symptomatic peripheral ischemia/ nerve injury with clinical signs or symptoms lasting >24 hours;
- Vascular surgical repair at catheter access sites;
- Pulmonary embolism;
- Ipsilateral deep vein thrombus; or
- Access site-related infection requiring intravenous antibiotics and/or extended hospitalization.

MYOCARDIAL INFARCTION

Myocardial infarction (MI) classification and criteria for diagnosis is defined as follows:

Peri-procedural MI (≤ 72 hours after MitraClip procedure)

Mandatory: CK-MB (preferred) ≥10x ULN within 72 hrs. post-MitraClip procedure in patient with normal baseline CK-MB

OR

Mandatory: CK-MB ≥5x ULN within 72 hrs. post-MitraClip procedure in patient with normal baseline CK-MB *plus* new pathological Q-waves in ≥2 contiguous leads, or new LBBB

Post-surgery

Mandatory: CK-MB ≥10x ULN (preferred) within 24 hrs. of cardiothoracic surgery *plus 1 of the following*:

- New pathological Q-waves in ≥2 contiguous leads or new persistent LBBB on ECG ≥30 min. and ≤72 hrs. post-CABG cardiothoracic surgery, or
- New substantial wall motion abnormalities by imaging except new septal or apical abnormalities.

Spontaneous MI (>72 hours after MitraClip procedure)

Any one of the following criteria:

- Detection of rise and/or fall of cardiac biomarkers (CK-MB) with at least one value above the upper limits of normal (ULN), together with evidence of myocardial ischemia with at least one of the following:
 - ECG changes indicative of new ischemia [new ST-T changes or new left bundle branch block (LBBB)]
 - New pathological Q waves in at least two contiguous leads

- Imaging evidence of new loss of viable myocardium or new wall motion abnormality
- Sudden, unexpected cardiac death, involving cardiac arrest, often with symptoms suggestive of myocardial ischemia, and accompanied by presumably new ST elevation, or new LBBB, and/or evidence of fresh thrombus by coronary angiography and/or at autopsy, but death occurring before blood samples could be obtained, or at a time before the appearance of cardiac biomarkers in the blood.
- Pathological findings of an acute myocardial infarction.

NEW YORK HEART ASSOCIATION CLASSIFICATION (NYHA CLASS)

Class I	Patients with cardiac disease but without resulting limitations of physical activity.
Class II	Patients with cardiac disease resulting in slight limitation of physical activity. Patients are comfortable at rest. Ordinary physical activity results in fatigue, palpitation, dyspnea, or anginal pain.
Class III	Patients with cardiac disease resulting in marked limitation of physical activity. Patients are comfortable at rest. Less than ordinary physical activity causes fatigue, palpitation dyspnea, or anginal pain.
Class IV	Patients with cardiac disease resulting in inability to carry on any physical activity without discomfort. Symptoms of cardiac insufficiency or of the anginal syndrome may be present even at rest. If any physical activity is undertaken, discomfort is increased.

NON-ELECTIVE (i.e., URGENT or EMERGENT) CARDIOVASCULAR SURGERY FOR PROCEDURE OR DEVICE RELATED EVENTS

Cardiovascular surgical procedure performed for device related complication requiring surgery within 24 hours of onset of adverse event, including events found during scheduled follow-up. If non-urgent surgery was performed within 24 hours of the onset of the adverse event but was not required within this timeframe, it will not be considered “non-elective”. Examples of Device Related Complications that may lead to non-elective cardiovascular surgery include, myocardial perforation, Single Leaflet Device Attachment (confirmed by Echo Core Lab), embolization of the MitraClip or MitraClip System components, iatrogenic atrial septal defect, or the need for valve replacement instead of repair due at least in part to the MitraClip procedure or the presence of the MitraClip.

SINGLE LEAFLET DEVICE ATTACHMENT (SLDA)

Defined as unilateral MitraClip detachment from one leaflet as assessed by the study site and confirmed by the ECL. Reasons for MitraClip Detachment include leaflet tearing, MitraClip unlocking, MitraClip fracture or inadequate MitraClip placement. Not included are any fractures or other failures of the MitraClip that do not result in MitraClip detachment from one or both leaflets.

STROKE/CEREBROVASCULAR ACCIDENT and TIA

Cerebrovascular Accident (Stroke) is defined as an acute episode of focal or global neurological dysfunction caused by brain, spinal cord, or retinal vascular injury as a result of hemorrhage or infarction. Stroke may be classified as ischemic or hemorrhagic with appropriate sub-definitions or as undetermined if there is insufficient information to allow categorization as ischemic or hemorrhagic.

An entity closely related to ischemic stroke is transient ischemic attack (TIA). TIA is defined as a transient episode of focal neurological dysfunction caused by brain, spinal cord, or retinal ischemia, without acute infarction. The difference between TIA and ischemic stroke is the presence of infarction. In the absence of affirmative evidence confirming the presence or absence of infarction, a symptom duration of 24 hours will be used to distinguish TIA from ischemic stroke. By definition, TIA does not produce lasting disability.

The assessment of disability resulting from the stroke will be performed by the modified Rankin Scale (mRS). Assessment of the mRS should occur at all scheduled visits through 24 months and at 90 days after stroke onset. This approach will maximize the detection of new strokes, assist in ongoing evaluation of events previously determined to be TIAs, and provide an accepted and reliable indicator of the long-term impact of a given stroke. A disabling stroke is one that results (at 90 days after stroke onset) in an mRS score of 2 or more and in an increase of at least one mRS category from the individual's pre-stroke baseline. A non-disabling stroke is one that results (at 90 days after stroke onset) in an mRS score of less than 2 or that does not result in an increase of at least one mRS category from an individual's pre-stroke baseline.

Although imaging (typically, MRI for acute and chronic ischemia and haemorrhage, and CT for acute and chronic haemorrhage and chronic ischemia) is often used to supplement the clinical diagnosis of stroke, a diagnosis of stroke may be made on clinical grounds alone.

Diagnostic criteria

Acute episode of a focal or global neurological deficit with at least one of the following: change in level of consciousness, hemiplegia, hemiparesis, numbness or sensory loss affecting one side of the body, dysphasia or aphasia, hemianopia, amaurosis fugax, or other neurological signs or symptoms consistent with stroke

Stroke – Duration of a focal or global neurological deficit ≥ 24 h; OR < 24 h if available neuroimaging documents a new hemorrhage or infarct; OR the neurological deficit results in death

TIA – Duration of a focal or global neurological deficit < 24 h, any variable neuroimaging does not demonstrate a new hemorrhage or infarct

No other readily identifiable non-stroke cause for the clinical presentation (e.g. brain tumor, trauma, infection, hypoglycemia, peripheral lesion, pharmacological influences), to be determined by or in conjunction with designated neurologist*

Confirmation of the diagnosis by at least one of the following:

- Neurologist or neurosurgical specialist
- Neuroimaging procedure (CT scan or brain MRI), but stroke may be diagnosed on clinical grounds alone

Stroke classification

Ischemic – An acute episode of focal cerebral, spinal, or retinal dysfunction caused by infarction of central nervous system tissue.

Hemorrhagic – An acute episode of focal or global cerebral or spinal dysfunction caused by intraparenchymal, intraventricular, or subarachnoid hemorrhage.

Undetermined – An acute episode where there is insufficient information to allow categorization as ischemic or hemorrhagic.

Stroke definitions†

Disabling stroke – a mRS score of 2 or more at 90 days and an increase of at least one mRS category from an individual's pre-stroke baseline

Non-disabling stroke – a mRS score of less than 2 at 90 days or one that does not result in an increase of at least one mRS category from an individual's pre-stroke baseline

*Patients with non-focal global encephalopathy will not be reported as a stroke without unequivocal evidence of cerebral infarction based upon neuroimaging studies (CT scan or Brain MRI).

†Modified Rankin Scale assessments should be made by qualified individuals according to a certification process.

Unanticipated Adverse Device Effect [UADE]

UADEs or Unanticipated serious adverse device effect (USADE) refers to any (serious) adverse effect on health or safety or any life-threatening problem or death caused by, or associated with, a device, if that effect, problem, or death was not previously identified in nature, severity, or degree of incidence in the protocol or application (including a supplementary plan or application), or any other unanticipated serious problem associated with a device that relates to the rights, safety, or welfare of subjects. All reported adverse events are reviewed by Sponsor so that UADEs/USADEs are identified and addressed.

VULNERABLE POPULATION (ISO14155 Definition)

Defined as subject whose willingness to volunteer in a clinical investigation could be unduly influenced by the expectation, whether justified or not, of benefits associated with participation or of retaliatory response from senior members of a hierarchy in case of refusal to participate. Examples of populations which may contain vulnerable subjects include: Individuals with lack of or loss of autonomy due to immaturity or through mental disability, persons in nursing homes, children, impoverished persons, subjects in emergency situations, ethnic minority groups, homeless persons, nomads, refugees, and those incapable of giving informed consent. Other vulnerable subjects may include, for example, members of a group with a hierarchical structure such as university students, subordinate hospital and laboratory personnel, employees of the sponsor, members of the armed forces, and persons kept in detention.

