Targeted number of subjects	Up to 1,000 subjects at a maximum of 60 sites in Europe and the US will be in the MitraClip EXPAND Study The study will group subjects into cohorts for analysis based upon pre-determined anatomical characteristics.
Study Design	Prospective, Multi-Center, Single-Arm, International, Post Market, Observational Study
Endpoints	
Safety
 
 Major Adverse Events (MAE) at 30 days 
Performance
 
 Mitral Regurgitation (MR) Reduction to $\leq 2+$ at 30 days 
Acute Measures:
 
 Acute Procedural Success (APS) Acute Device Success Procedure Time Device Time Number of Clips Implanted Number of Attempted Grasps Use of MitraClip NTR or MitraClip XTR Device-Related Complications User Feedback In-hospital MAE MR Reduction to $\leq 1+$ at 30 days 
Clinical Measures (Discharge, 1, 6 and 12 months):
 
 All-cause Mortality Heart Failure Hospitalization MAE Device-Related Complications 
Functional improvement Measures (Baseline, Discharge & 12 months):
 
 New York Heart Association (NYHA) class improvement Quality of Life (QOL) improvement conducted by Kansas City Cardiomyopathy Questionnaire (KCCQ)

	
Echo Measures (Baseline, Post Procedure, 1, & 12 months): Based on Site Reported Echocardiogram data for all subjects
 
 • MR Severity Grade • Effective Regurgitant Orifice Area (EROA) • Coaptation Measures (length and depth) • Flail Measures (gap and width) • Grasping Area Anatomy • Chordal Support • Regurgitant Jet(s) Position and Quantity • Tricuspid Regurgitant (TR) Severity 
Core Lab Subgroup: Echocardiograms from a minimum of 100 subjects will be sent to a Core Lab for assessment

Subject Follow-up	
Echocardiogram: Discharge, 30 days and 12 Months Clinical Visit: 30 days and 12 Months Phone Call: 6 Months

Inclusion Criteria	
 1. Subjects who give consent for study participation 2. Subjects scheduled to receive the MitraClip per the current approved indications for use 3. Subjects with Symptomatic MR (≥3+)
Exclusion Criteria	
 1. Subjects participating in another clinical study that may impact the follow-up or results of this study.

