3.2 Overall Flow of the Study and Follow-up Schedule

[figure not shown]
Enrolled patients that receive a MitraClip implant should undergo study follow-up per standard of care. Follow-up data on clinical assessment should be submitted for a 30-day visit, 6-month visit or phone call and 12-month visit. Echocardiograms are required to be submitted for the baseline, discharge, 30-day and 12-month time points. All Echocardiograms conducted during the study period (required by protocol or not) will be collected by the Sponsor (see **Table 2** for the Clinical Assessment Schedule). Patients that have an attempted procedure, but no MitraClip implant will be followed for 30 days only.

The first 220 European patients treated with the MitraClip XTR in *the MitraClip EXPAND Study* with evaluable APS data will be included in the XTR PMCF Study as described in Appendix 1.

Subjects with evaluable echocardiograms may be selected for a more detailed assessment by an independent core lab. Pre-defined criteria will be used to identify eligible subjects for this assessment. A minimum of 100 subjects will be randomly selected from this eligible population.

Figure 3 outlines the flow of the Study.

Figure 3: Study Flow

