4.5 Site Reported Echocardiographic Measures

(Baseline, Post Procedure, 1, & 12 months):

- MR Severity Grade
- Effective Regurgitant Orifice Area (EROA) as measured by measured by PISA method
- Coaptation Measures (depth/length)

- *Coaptation depth: Coaptation depth is defined as the distance from the plane of the mitral valve annulus to the first point of leaflet coaptation in the atrial-to-ventricular direction in the four-chamber view.*
- *Coaptation length: Coaptation length is defined as the vertical length of leaflets that is in contact, or is available for contact, during systole in the atrial-to-ventricular direction in the four-chamber view.*
- Flail Measures (gap/width)
 - *Flail Gap: Measured as the greatest distance between the ventricular side of the flail segment to the atrial side of the opposing leaflet. This distance is measured perpendicular to the plane of the annulus in two views and the largest measurement is used. The two views for measurement are the four-chamber long axis (LAX) view and the left ventricular outflow tract (LVOT) view.*
 - *Flail Width: Measured as the width of the leaflet segment that moves in and out of plane during systole in the short axis (SAX) view.*
- Grasping Area Anatomy (measure cleft or scallop if significant)
- Assess chordal support
- Regurgitant Jet(s) Position and Quantity
- TR Severity: None, Mild, Moderate or Severe

4.6 Core Lab Subgroup:

Subjects with evaluable echocardiograms may be selected for a more detailed assessment by an independent core lab. Pre-defined criteria will be used to identify eligible subjects for this assessment. A minimum of 100 subjects will be randomly selected from this eligible population.

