8.0 ADJUDICATION OF EVENTS

8.1 The Clinical Events Committee (CEC)

A Clinical Events Committee is comprised of qualified physicians who are not investigators in the study. The CEC will review and adjudicate pre-specified events reported by investigators or identified by the Safety & Surveillance personnel/designate for the study as documented in a CEC Manual of Operations (MOP).

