4.2 Clinical Endpoints

Clinical Endpoints will be assessed at each study time point, all data reported at the corresponding study visit will be included for the study time point.

- Major Adverse Events (MAE): defined as a composite of CEC adjudicated all-cause Death, Myocardial Infarction, Stroke, or non-elective CV surgery for device related complications
- MR Severity
- Device Related Adverse Events (including mitral valve stenosis, device embolization, single leaflet device attachment (SLDA), iatrogenic atrial septal defect, myocardial perforation, or the need for mitral valve replacement instead of repair due at least in part to the MitraClip procedure or the presence of the MitraClip device)
- All-cause mortality
- Recurrent heart failure hospitalization
- New York Heart Association (NYHA) functional class improvement

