6.3 Post-procedure

Post treatment TTEs/TEES, Clinical Assessments and Laboratory / Clinical Tests should be conducted per standard of care. Post-procedure information to be reported for this study include at minimum: adverse events, MR severity and New York Heart Association (NYHA) Functional Class.

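### SLDA is defined as confirmed by the core lab, but core-lab reading is committed only for a random minimum of 100 of up to 1,000 subjects, and no visible rule covers an unread case

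*Protocol*

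**What the plan says.** **Definition.** Protocol Appendix III and Appendix II of the XTR PMCF protocol (Protocol Appendix I) give the same SLDA definition: "Defined as unilateral MitraClip detachment from one leaflet as assessed by the study site and confirmed by the ECL". The two conditions are joined by *and*. In the same appendices, device embolization needs only the study site's assessment.

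**Core-lab reading.** The Protocol Summary says "Echocardiograms from a minimum of 100 subjects will be sent to a Core Lab for assessment". Sections 3.2 and 4.6 say "Subjects with evaluable echocardiograms may be selected for a more detailed assessment by an independent core lab", refer to pre-defined eligibility criteria that are not given, and add "A minimum of 100 subjects will be randomly selected from this eligible population". The analysis set is up to 1,000 subjects (section 3.1). Echo measures for all subjects are site reported (Protocol Summary, section 4.5).

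**Where SLDA is used.**
- Protocol 4.2 and SAP 1.4.2 list SLDA in Device-Related Complications. They also list it among the events whose occurrence through discharge defeats Acute Device Success.
- Section 4.2 of the PMCF protocol has an endpoint "Device Related Adverse Events (including mitral valve stenosis, device embolization, single leaflet device attachment (SLDA), iatrogenic atrial septal defect, myocardial perforation", and further events. The PMCF text describes no core-lab reading.

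**What is collected.** The sponsor collects every echocardiogram done during the study, including unscheduled ones (sections 3.2 and 6.4.1).

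**Missing data.** SAP 2.8 uses available data without imputation. It does not mention an SLDA that the core lab has not read.

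**The concern.** The definition needs a core-lab read for each reported SLDA, but the reading plan does not promise one. Selection is random within an eligible pool and is not triggered by an event. No visible passage routes a site-reported SLDA to the core lab.

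The analyst is left with two courses. If the definition is followed literally, an unread SLDA is not an event, and the error runs in the device's favour: fewer Device-Related Complications, fewer PMCF Device Related Adverse Events and higher Acute Device Success. If unread cases are counted anyway, the reported endpoint departs from its written definition. In both cases the rule could end up being chosen after the data have been seen.

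The question matters for these devices. The study is meant to confirm safety of systems not yet evaluated in a clinical study, and the XTR's longer arms are intended to help leaflet grasping, so attachment failure is directly relevant.

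**Working it through.** The documents give no calculation behind the minimum of 100, so there is no plan figure to reproduce. The check is one of coverage.

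**Inputs**
- N = 1,000 subjects (upper limit, Protocol 3.1) and n = 100 reads (minimum, Protocol 4.6).
- r = site-reported SLDA rate. The EXPAND rate is unknown, so rates reported in Protocol Appendix IV serve as assumptions. They come from earlier devices with differing follow-up:
  - none: the GRASP registry reported no clip detachment
  - 0.7%: TRAMI registry
  - 1.5%: one-year TVT Registry report
  - 4.3%: REALISM non-high-risk arm (check: 11/258 = 4.26%)
  - 10%: EVEREST I, the earliest cohort

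**Step 1, coverage.** n/N = 100/1,000 = 10%, so 90% of SLDAs would be unread if SLDA cases are as likely to be selected as other subjects.

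**Step 2, gap in the SLDA contribution to Device-Related Complications under literal application.** Gap (percentage points) = 100 × r × (1 − n/N), assuming that the core lab confirms every SLDA it reads.

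| r | Site-reported per 1,000 | Unread at n = 100 | Gap at n = 100 | Gap at n = 500 | Gap if every reported SLDA is read |
|---|---|---|---|---|---|
| 0% | 0 | 0 | 0 | 0 | 0 |
| 0.7% | 7 | 6.3 | 0.63 | 0.35 | 0 |
| 1.5% | 15 | 13.5 | 1.35 | 0.75 | 0 |
| 4.3% | 43 | 38.7 | 3.87 | 2.15 | 0 |
| 10% | 100 | 90 | 9.0 | 5.0 | 0 |

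The column for 500 reads is there because 100 is a floor; the documents do not state that number.

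**Step 3, does the missing-data rule settle it?** Take r = 4.3% and n = 100, so 43 reported cases, of which 4.3 are read and 38.7 are not.
- Unread counted as events: 43/1,000 = 4.3%.
- Unread counted as non-events: 4.3/1,000 = 0.43%.
- Unread excluded as missing: 4.3/(1,000 − 38.7) = 4.3/961.3 = 0.45%.

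SAP 2.8 does not choose among these. Excluding unread cases as missing gives almost the same low rate as calling them non-events.

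**Step 4, Acute Device Success.** Only events through discharge count, so its gap is no larger than the figures in Step 2.

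**The case against.** The strongest reply is that the core lab has two separate jobs. The subgroup is for a more detailed assessment. The SLDA definition is an event rule, and it could itself be taken to require a core-lab look at each site-reported case. The images are in hand because the sponsor collects them all. SAP 1.4.6 lists core-lab measures with no subgroup limit, and adjudication of pre-specified events is "documented in a CEC Manual of Operations (MOP"), which is not available here. The SAP also cites a differently numbered plan, so the gap may come from the set of documents in view.

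Part of this stands. The minimum of 100 is a floor, and wider or event-triggered reading is quite possible. But collecting images commits nobody to reading them. SAP 1.4.6 gives no number of subjects and does not list SLDA. A further reply, that Protocol 4.2 leaves the matter to the investigator, fails: that wording assigns the investigator the relation to the device, not confirmation that an SLDA occurred.

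A reader might go further and infer three things that the documents do not support:
- *That unread SLDAs will be dropped.* No passage states such an exclusion. It follows only if the definition is applied literally and reads are confined to the subgroup.
- *That the 30-day MAE endpoint is gated by the core lab.* The phrase "Single Leaflet Device Attachment (confirmed by Echo Core Lab") appears under non-elective surgery only in a list of examples. SLDA is not itself a component of MAE, MR reduction or APS.
- *That the number of random reads needed, or the number of PMCF subjects read, can be calculated.* Selection is from a pool set by unseen criteria. Reading the reported cases alone would close the gap.

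**Conclusion.** The point holds as a conflict between the SLDA definition and the visible reading plan. At the committed minimum, literal application would leave about 90% of site-reported SLDAs unable to qualify. The resulting gap is about 0.6 percentage points at a 0.7% rate, 3.9 at 4.3% and 9 at 10%. It is zero if no SLDA occurs or if every reported one is read.

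These figures are illustrations. They assume 1,000 subjects, selection unrelated to SLDA, core-lab confirmation of every case read, all SLDAs judged at least possibly device related, and background rates carried over from earlier devices. Because a subject may have another qualifying complication, the effect on the composite can be smaller than the SLDA gap.

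The reach is limited to descriptive secondary safety measures. Site-reported events would still appear in the adverse event tables of SAP 3.2. That makes this a change that should be made, not a threat to the headline 30-day endpoints.

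**What to change.** In both definition appendices and in SAP 1.4.2, add one sentence: a site-reported SLDA counts as an event, subject to the existing device-relatedness condition, unless the core lab has read the echocardiogram and not confirmed it. It then counts in Device-Related Complications and the PMCF Device Related Adverse Events, and as a failure in Acute Device Success through discharge. Report core-lab-confirmed SLDA separately, with the number of cases read as its denominator.

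Alternatively, if that is the intent, state in Protocol 4.6 and SAP 1.4.6 that the core lab reads every site-reported SLDA from the echocardiograms already collected. This keeps the present definition and a single standard of evidence. On the rates above other than zero and 10%, it means about 7 to 43 cases per 1,000 subjects; at 10% it would be 100.

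The first option costs three sentences and one table row, with no extra reads. Its downside is that some counted SLDAs lack independent confirmation, refutation is possible only where a read exists, and the reported rate may be less favourable.
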